3.1. Summary of Study Design

This study is being conducted in the same population as in the emergency use authorization (EUA) (FDA 2020).

Study J2X-MC-PYAJ is an open-label, prospective, single-arm observational study in participants with mild to moderate COVID-19 (see Section 3.3.1 for criteria). Study participants who received a one-time IV infusion of bamlanivimab (LY3819253) within 10 days of symptom onset and following the first positive severe acute respiratory syndrome coronavirus 2 (SARS-CoV-2) test sample collection will then be followed for 90 days to assess any additional medical care needed or if hospitalization was required (Figure 3.1).

Abbreviation: EMR = electronic medical record.

^a Screening and Day 1 procedures may occur on the same day.

^b Telephone call 24 hours post-infusion.

^c EMR review and phone call.

Figure 3.1 Study J2X-MC-PYAJ study design.

Screening

Interested participants or their legally authorized representative will sign the appropriate informed consent and adolescent assent document(s), as appropriate, prior to completion of any procedures.

The investigator will confirm a positive reverse transcription-polymerase chain reaction (RT-PCR) test or antigen testing confirmation for COVID-19 (if antigen test is accompanied by symptoms suggestive of SARS-CoV-2 infection) and complete baseline procedures to confirm eligibility per inclusion and exclusion criteria and review criteria for high risk under the EUA.

Treatment and Assessment Period

This is the general sequence of events during the treatment and assessment period:

- participants receive study intervention, and
- complete all safety monitoring and post-infusion data collection.

Treated Population Visit Types

The visit types for the Treatment Population table in Section 4.1 of the protocol describes the visit types for the treatment population for this study.

Guidelines if a Participant is Hospitalized

If a participant is hospitalized, procedures and assessments will continue per the Schedule of Activities (SoA) (Study PYAJ Protocol Section 1.3).

The Description of Discharge from Hospital Scenarios table in Section 4.1 of the protocol describes discharge from hospital scenarios if an outpatient is subsequently hospitalized.

Post-treatment

Post-treatment assessments will be conducted at Days 2, 29, 60, and 90 to assess study endpoints.

3.2. Data Collection

Data for bamlanivimab-treated patients will be captured at the infusion visit (Day 1), at 24 hours post-infusion (Day 2), and at subsequent follow-up periods (Days 29, 60, and 90). Case report form (CRF) data documented within the EDC system will be captured on-site on Day 1 and via telephone call on Days 2, 29, 60, and 90. The EMR records will be extracted during 1 year prior to and 90 days post the infusion date.

Sample Size Determination

Due to early termination, the study enrolled 109, rather than the anticipated 500-3000, bamlanivimab-treated patients. Given that the revised primary objective is to determine the proportion of patients with COVID-19-related hospitalization or all-cause death up to 29 days among bamlanivimab-treated participants and without the use of a comparison group, the observed sample size was 109 participants. This achieved sample size of 109 participants will allow for estimating the proportion with a precision of $\pm 4.4\%$ ($=1.96*\sqrt{(p(1-p)/n)}$) under the assumption of normal approximation of a binomial distribution at a 2-sided significance level of 0.05 and 6% of the true rates of COVID-19-related hospitalization or all-cause death.

3.3. Study Population

3.3.1. Selection Criteria

Prospective approval of protocol deviations to recruitment and enrollment criteria, also known as protocol waivers or exemptions, is not permitted.

Due to the criticality of participant health, verbal interview of the potential participant, or their legal representative or family member, may be the source for disease characteristics and medical history, unless otherwise specified within the eligibility criteria.

Inclusion Criteria:

Participants are eligible to be included in the study only if all of the following criteria apply:

Age

1. Are ≥ 12 years of age at the time of screening

Disease Characteristics

2. Are currently not hospitalized
3. Have one or more mild or moderate COVID-19 symptoms (FDA 2020)
 - i. Fever
 - ii. Cough
 - iii. Sore throat
 - iv. Malaise
 - v. Headache
 - vi. Muscle pain
 - vii. Gastrointestinal symptoms, or
 - viii. Shortness of breath with exertion.
4. Must have first positive SARS-CoV-2 viral infection determination and as soon as possible within 10 days of symptom onset
5. Are males or non-breastfeeding females Reproductive and Contraceptive agreements and guidance is provided in the protocol Section 10.3, Appendix 3. Contraceptive use by males or females should be consistent with local regulations for those participating in clinical studies

Study Procedures

6. Understand and agree to comply with planned study procedures

Informed Consent

7. The participant or legally authorized representative gives signed informed consent and/or assent as described in the protocol Section 10.1.3, which includes compliance with the requirements and restrictions listed in the Informed Consent Form (ICF) and in the protocol

High risk as defined per EUA fact sheet (FDA 2020)

8. For example, participants who meet at least 1 of the following criteria:
 - Have a body mass index (BMI) ≥ 35
 - Have chronic kidney disease
 - Have diabetes
 - Have immunosuppressive disease
 - Are currently receiving immunosuppressive treatment
 - Are ≥ 65 years of age
 - Are ≥ 55 years of age AND have
 - cardiovascular disease, OR
 - hypertension, OR
 - chronic obstructive pulmonary disease or other chronic respiratory disease.
 - Are 12–17 years of age AND have

- BMI \geq 85th percentile for their age and gender based on Centers for Disease Control and Prevention (CDC) growth charts, https://www.cdc.gov/growthcharts/clinical_charts.htm, OR
- sickle cell disease, OR
- congenital or acquired heart disease, OR
- neurodevelopmental disorders, for example, cerebral palsy, OR
- a medical-related technological dependence, for example, tracheostomy, gastrostomy, or positive pressure ventilation (not related to COVID-19), OR
- asthma, reactive airway or other chronic respiratory disease that requires daily medication for controls.

3.3.2. Exclusion Criteria:

Limitations of Benefit and Potential for Risk in Patients with Severe COVID-19

Benefit of treatment with bamlanivimab has not been observed in patients hospitalized due to COVID-19. Monoclonal antibodies, such as bamlanivimab, may be associated with worse clinical outcomes when administered to hospitalized patients with COVID-19 requiring high flow oxygen or mechanical ventilation. More specifically, participants are excluded from the study if any of the following criteria apply:

Medical Conditions

9. Participants who:
 - a) are hospitalized due to COVID-19,
 - b) require oxygen therapy due to COVID-19, OR
 - c) require an increase in baseline oxygen flow rate due to COVID-19 in those on chronic oxygen therapy due to underlying non-COVID-19-related comorbidity.
10. Have SpO₂ \leq 90% on room air or PaO₂/FiO₂ $<$ 300, respiratory rate \geq 30 per minute, heart rate \geq 125 per minute (FDA 2020)
11. Have body weight $<$ 40kg
12. Require mechanical ventilation or anticipated impending need for mechanical ventilation
13. Have known allergies to any of the components used in the formulation of the interventions
14. Suspected or proven serious, active bacterial, fungal, viral, or other infection (besides COVID-19) that in the opinion of the investigator could constitute a risk when taking intervention
15. Have any comorbidity requiring surgery within $<$ 7 days, or that is considered life-threatening within 29 days
16. Have any serious concomitant systemic disease, condition, or disorder that, in the opinion of the investigator, should preclude participation in this study

Other Exclusions

17. Have a history of a positive SARS-CoV-2 serology test
18. Have a history of a positive SARS-CoV-2 test prior to the one serving as eligibility for this study

19. Have received an investigational intervention for SARS-CoV-2 prophylaxis within 30 days before dosing
20. Have received treatment with a SARS-CoV-2-specific monoclonal antibody, remdesivir, or other treatment for COVID-19
21. Have received convalescent COVID-19 plasma treatment
22. Have participated in a previous SARS-CoV-2 vaccine study
23. Have participated, within the last 30 days, in a clinical study involving an investigational intervention. If the previous investigational intervention has a long half-life, 5 half-lives or 30 days, whichever is longer, should have passed.
24. Are concurrently enrolled in any other type of medical research judged not to be scientifically or medically compatible with this study
25. Are breast-feeding
26. Are investigator site personnel directly affiliated with this study

3.4. Patient Group

There is 1 study population: participants treated with bamlanivimab.

3.5. Endpoints

The study endpoints are defined as at 29, 60, and 90 days of the date of the bamlanivimab infusion.

[figure not shown]

Figure 3.2. Illustration of the timeline for study participants.

The following endpoints are defined based on the EDC and EMR data.

- Primary endpoint:
 - COVID-19-related hospitalization (defined as ≥ 24 hours of acute care for COVID-19) or all-cause death up to 29, 60, and 90 days
- Secondary endpoints:
 - COVID-19-related hospitalization, defined as ≥ 24 hours of acute care, up to 29, 60, and 90 days
 - COVID-19-related emergency department (ED) visits up to 29, 60, and 90 days
 - Adverse Events (AEs) or Severe Adverse Events (SAEs) up to 2 hours, 24 hours, and 29, 60, and 90 days

The period of follow-up for ascertainment of these endpoints will be 29, 60, and 90 days following the infusion date. The COVID-19-related hospitalization or all-cause death will be

defined as binary, and secondarily time to event variable will also be included. For time-to-event endpoints, days to the first COVID-19-related hospitalization or death will be calculated from the infusion date. For patients who do not experience a particular endpoint up to 29, 60, and 90 days following the infusion date, a censoring date will be defined as the earliest of

- 29, 60, and 90 days following the infusion date, or
- the early discontinuation date (study participants).

The AEs or SAEs will be collected from the CRF. The proportion of patients with an SAE or AE will be reported.

3.6. Study Therapies

Bamlanivimab (LY3819253) is a neutralizing IgG1 monoclonal antibody to the spike protein of SARS-CoV-2. It is designed to block viral attachment and entry into human cells, thus neutralizing the virus, potentially preventing and treating COVID-19.

3.7. Variables/Measures

The following variables will be defined based on the EDC/EMR data.

Table 3.1 Variable Definitions/Data Source

Variables	Definition	Data Source
Demographics		
Age at index date, year	Age: whole numbers calculated from bamlanivimab index date Age group: Age ≥ 65 ; Age 55 to 64; Age 18 to 54; and Age 12 to 17	From EMR
Sex	Female and male	From EMR
Race	American Indian / Alaskan Native Asian Black / African American Native Hawaiian / Pacific Islander White Multiple	
Ethnicity	Hispanic, non-Hispanic	
Weight, kg	Continuous variable	
Height, cm	Continuous variable	
BMI	Calculated as $BMI = \text{kg}/\text{m}^2$ where kg is a person's weight in kilograms and m^2 is their height in meters squared. Continuous and categorical ≤ 25 ; 25 to < 30 ; and ≥ 30	From EMR
Tobacco use	current use, former, and never	
Vital signs	
 • body temperature • pulse rate • systolic blood pressure • diastolic blood pressure • respiratory rate • SpO₂ 	From EMR

Variables	Definition	Data Source
	
 supplemental oxygen flow rate FiO2 and method of delivery, if applicable 	
COVID-19 symptoms	
Total of 8-binary indicator variables will be created for the below symptoms:
 
 fever cough sore throat malaise chills loss of sense of taste loss of sense of smell fatigue. headache muscle pain gastrointestinal symptoms shortness of breath with exertion 
The date of COVID-19 symptom onset is defined as the earliest start date of symptoms suggestive of SARS-CoV-2 infection; calculated by difference of bamlanivimab index date and reported symptom date
	From EMR
Days since COVID-19 symptom onset.	Calculated as the difference index date and COVID-19 symptom onset date. Category: ≤8 days and >8 days	
Type of COVID-19 diagnosis test	RT-PCR, antigen testing COVID-19 diagnosis date	
Preexisting conditions and medical history during 1 year prior to the infusion	
Binary indicator variables will be created for the below:
 
 chronic kidney disease diabetes (type I, type II) immunosuppressive disease currently receiving immunosuppressive treatment cardiovascular disease hypertension chronic obstructive pulmonary disease or other chronic respiratory disease sickle cell disease congenital or acquired heart disease neurodevelopmental disorders medical-related technological dependence; for example, tracheostomy, gastrostomy, or positive pressure ventilation (not related to COVID-19) asthma, reactive airway or other chronic respiratory disease that requires daily medication for controls 	From EMR

Variables	Definition	Data Source
Treatments of special interest prescribed within 30 days prior to infusion (exclusive infusion date)	Dates of: 
 • NSAIDs • antivirals • antibiotics • anti-malarials • corticosteroids • immunomodulators • other investigational treatments (including ivermectin, COVID-19 vaccine, and oxygen) 	From EMR
Prior or concomitant therapy 90 days before and 90 days after infusion	Dates of: 
 • NSAIDs • antivirals • antibiotics • anti-malarials • corticosteroids • immunomodulators 	From EMR
Procedures of special interest during 10 days prior infusion	Dates of: 
 • supplemental oxygen • non-invasive ventilation • high flow oxygen device • mechanical ventilation • Extracorporeal membrane oxygenation (ECMO) • additional organ support 	From EMR
Respiratory support	Dates of: 
 • high flow nasal cannula • noninvasive positive pressure ventilation 	From EMR
Mortality	
 • date • cause of death 	From EMR
Pregnancy	Date of confirmed pregnancy	From EMR

Abbreviations: BMI = body mass index; COVID-19 = coronavirus disease 2019; EMR = electronic medical record; FiO₂ = fraction of inspired oxygen in the air; NSAID = nonsteroidal anti-inflammatory drug; RT-PCR = reverse transcription-polymerase chain reaction; SARS-CoV-2 = severe acute respiratory syndrome coronavirus 2; SpO₂ = saturation of peripheral oxygen.

4. Statistical Analyses

4.1. General Considerations

All analyses will be conducted on bamlanivimab-treated study participants.

Descriptive analysis will be conducted without imputation of missing values. Categorical variables will be summarized using frequencies and proportions. Continuous variables will be summarized using mean with standard deviations, and medians with interquartile range.

Additional exploratory analyses of the data will be conducted as deemed appropriate.

All statistical analyses will be performed using SAS software Version 9.4 (or a higher version).

4.2. Participant Dispositions

The number and percentage of study participants who complete the study or discontinue early will be tabulated up to 29, 60, and 90 days follow-up. Reasons for discontinuation will be summarized.

4.3. Populations for Analyses

The analysis population includes all patients who meet inclusion criteria and receive bamlanivimab in a single IV infusion of 700 mg or less.

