### 9.3. Populations for Analyses

This table defines the populations for analysis.

Population	Description
Entered	All participants who sign the informed consent form.
Efficacy	All participants who received study intervention and provided at least one post-baseline measure for the relevant endpoint. Participants will be analyzed according to whether they received the study intervention (treated group, control group).
Safety	All participants who received study intervention.

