##### **9.4.1.1. Safety analysis**

- COVID-19 related hospitalization, defined as  $\geq 24$  hours of acute care, up to Days 60 and 90
- ED visits for COVID-related causes
- AEs/SAEs

Safety analyses will be conducted using the safety population described in Section 9.3.

All investigational product and protocol procedure AEs will be listed, and if the frequency of events allows, safety data will be summarized using descriptive methodology.

The incidence of AEs will be presented by severity and by association with intervention as perceived by the investigator, regardless of ascertainment of relatedness.

Safety parameters that will be assessed include AEs and SAEs. The parameters will be listed and summarized using standard descriptive statistics.

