The number and percentage of participants who experienced an AE, SAE, AE related to study drug, died due to an AE, discontinued from the study treatment, or discontinued from the study due to an AE will be summarized by during infusion and after infusion for up to 2 hours, 24 hours, 29 days, 60 days, and 90 days. The summary method for each event type is described in [Table 4.1](#).

Table 4.1 Types of Adverse Events to be Summarized

Event Type	Summary Method
SAE	SAEs will be summarized for study participants by SOC and PT. These reports will also include the total number of SAE for each SOC and PT.
AE Resulting in Death	If there are any AEs that result in death, a listing of all deaths will be provided. In addition, a summary table may also be created by PT in order of decreasing frequency of PT.
AE Leading to Study Drug Discontinuation	AEs for which the action taken with medication as 'Drug Withdrawal' will be identified as AEs that lead to study drug discontinuation. The AEs that lead to study drug discontinuation will be summarized by SOC and PT for the safety population. A by-patient listing of the AEs that lead to study drug discontinuation will also be provided.
Treatment-Related AE	Every AE will be assessed by the investigator for its relationship to the study treatment.
AE by Maximal Severity	Every AE will be graded by the investigator as mild, moderate, or severe, so for each patient the greatest severity observed can be obtained by comparing the severity of all of a patient's AEs that share the same SOC or PT. A table of AEs by maximal severity will be prepared by SOC and PT.
AE (Not Including Serious)	The most common, nonserious AEs will be summarized. All PTs that occur in at least 1% of the safety population participants, when not counting the serious AEs, will be tabulated by SOC and PT. These reports will also present the total number of AEs for each SOC and PT.

Abbreviations: AE = adverse event; PT = Preferred Term; SAE = serious adverse event;
SOC = System Organ Class.

Infusion Site Reactions

Infusion site reactions are AEs localized to the immediate site of the administration of a drug and will be defined using terms from the MedDRA High-Level Term, Infusion Site Reactions. All ISRs will be listed.

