Vital signs data will be summarized by box plots for observed values, along with changes from baseline by timepoints.

Box plots for observed values by timepoints will include participants with a non-missing value at the timepoint. Values outside 1.5 interquartile range (IQR) below 25% and above 75% will be shown as outliers. Descriptive summary statistics will be included in a table below the box plot.

Box plots for change from baseline values to each post baseline timepoints will be presented similarly to those for observed values by timepoints described above. They will include participants with a non-missing value at the timepoint, and values outside 1.5 IQR below 25% and above 75% will be shown as outliers. Descriptive summary statistics will be included in a table below the box plot.

All vital signs and other physical findings for individual participants will be listed.

Protocol Violations

Protocol violations will be identified throughout the study. Important protocol deviations (IPDs) are defined as those deviations from the protocol that would potentially compromise participants' safety, data integrity, or study outcome.

The number and percentage of participants having IPDs will be summarized within each category and subcategory of deviations. A by-patient listing of IPDs will be provided.

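### The SAP's only analysis set is narrower than the protocol's Safety population, conflicts with other SAP sections, and is not declared as a change

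*SAP*

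**What the plan says.** **Protocol.** Section 9.3 defines the Safety population as "All participants who received study intervention". The Efficacy population adds only that the participant "provided at least one post-baseline measure for the relevant endpoint". Neither carries an eligibility or dose condition. Section 9.4.1.1 then states: "Safety analyses will be conducted using the safety population described in Section 9.3".

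**SAP.** Section 4.3 defines a single set: "The analysis population includes all patients who meet inclusion criteria and receive bamlanivimab in a single IV infusion of 700 mg or less". Three other places in the SAP bear on the same question:

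- Section 3.4: "There is 1 study population: participants treated with bamlanivimab".
- Section 4.1: "All analyses will be conducted on bamlanivimab-treated study participants".
- Section 4.5, Table 4.1, uses the term safety population twice. One use sets the display rule for nonserious events: "All PTs that occur in at least 1% of the safety population participants". The SAP does not define the term.

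Section 4.5 also plans a deviation summary: "The number and percentage of participants having IPDs will be summarized within each category and subcategory of deviations". Section 4.9, which lists departures from the protocol's planned analyses, covers only the loss of the control group and the move to descriptive analysis.

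**The concern.** The SAP does not settle who enters the safety summaries. Sections 3.4 and 4.1 point to everyone treated, while 4.3 points to a subset. Two programmers could follow different sections and produce different denominators.

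If 4.3 governs, it removes treated patients who missed an inclusion criterion and patients who received more than 700 mg. The protocol foresees both cases: 7.2.1 deals with inadvertent enrollment and 8.4 with an excess dose. The rule is also uneven, because it names inclusion criteria only. A treated patient who met an exclusion criterion stays in.

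Safety is a stated objective of what is now a descriptive single-arm report, so AE and SAE percentages should cover everyone exposed, as the protocol requires. The summary of important protocol deviations (IPDs) has a further problem. Under 4.3, an inclusion failure or an excess dose that counts as an IPD would be absent from the summary meant to report it.

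**Working it through.** **Comparing the definitions**

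| Source | Treated | Meets inclusion criteria | Single infusion of 700 mg or less | Post-baseline measure |
|---|---|---|---|---|
| Protocol 9.3 Safety | yes | – | – | – |
| Protocol 9.3 Efficacy | yes | – | – | yes |
| SAP 3.4 and 4.1 | yes | – | – | – |
| SAP 4.3 | yes | yes | yes | – |

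The SAP 4.3 set is a subset of protocol Safety. The two coincide only if no treated patient fails an inclusion criterion or breaches the dose condition. Against protocol Efficacy, 4.3 is narrower on two conditions and wider on one.

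**Inputs.** n = 109 treated (SAP 4.7). The event rate of 6% and the multiplier 1.96 come from the SAP's Sample Size Determination text. The number excluded under 4.3 is not given, so I assume a range of 0 to 10.

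**The SAP's own figure.** Half-width = 1.96 × √(p(1 − p)/n) = 1.96 × √(0.06 × 0.94/109) = 4.46 points. The SAP prints ±4.4%, which is this value truncated. The difference has no bearing here, but the calculation does use all 109.

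**Effect of a smaller denominator, same formula**

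| Excluded (assumed) | n | Half-width (points) |
|---|---|---|
| 0 | 109 | 4.46 |
| 1 | 108 | 4.48 |
| 5 | 104 | 4.56 |
| 10 | 99 | 4.68 |

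Over the whole range the change is 4.68 − 4.46 = 0.22 points.

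**Effect of losing an event: the 1% display rule in Table 4.1**

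- A nonserious preferred term in 2 patients: 2/109 = 1.83%, displayed.
- One of those two patients excluded: 1/108 = 0.93%, not displayed.
- A term in a single patient reaches 1% only when n is 100 or less, that is, after at least 9 exclusions.

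**Effect of losing an event: an SAE in one patient (exact Clopper-Pearson 95% limits)**

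- All treated: 1/109 = 0.92% (0.02% to 5.01%).
- That patient excluded: 0/108, upper limit 1 − 0.025^(1/108) = 3.36%.
- Five excluded, including that patient: 0/104, upper limit 1 − 0.025^(1/104) = 3.48%.
- Ten excluded, including that patient: 0/99, upper limit 1 − 0.025^(1/99) = 3.66%.

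**The case against.** The strongest reply is that the intended set is clear and 4.3 is only loosely worded. SAP 3.4 and 4.1 say treated participants, the precision statement uses 109, and no other analysis number appears anywhere. The dose phrase may have been meant to keep partial infusions in, which fits the planned count of incomplete infusions in 4.5. The Version 2 revision history records that the population was updated to treated patients only. The term in Table 4.1 can be read as importing Protocol 9.3.

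The intent may well have been all treated patients. That supports correcting 4.3, because the section as written sets conditions that a programmer would code. The revision entry agrees with 3.4 and 4.1 and does not disclose the inclusion or dose conditions. Importing the protocol definition would settle only the two Table 4.1 entries that use the term, and the SAP does not say that it does so.

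Several limits on the impact stand:

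- Nothing shows that any of the 109 is affected. Eligibility waivers are barred, and a second staff member confirms each dose.
- The AE, death and vital-sign listings would give partial cover, and SAEs have no display threshold.
- The loss from the IPD summary follows only if 4.3 overrides 4.1.
- Using all treated patients for the primary proportion itself departs from the protocol Efficacy set. It must be declared, with a rule for treated patients who have no follow-up, since SAP 4.6 bases summaries on nonmissing data.

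**Conclusion.** The concern holds and should be fixed. SAP 4.3 is narrower than the set the protocol requires for safety analyses, it conflicts with SAP 3.4 and 4.1, it leaves the safety population in Table 4.1 undefined, and 4.9 does not declare the change. These conclusions come from comparing the definitions and rest on no assumption.

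The numerical effect is uncertain and may be nil. With 0 to 10 exclusions assumed, the loss of precision is at most 0.22 points. The material risk is an event dropping out with an excluded patient: a nonserious term in two patients can vanish from Table 4.1, and a lone SAE can become zero, with its upper limit falling from 5.01% to 3.36%. Both examples are hypothetical. No view is taken on the dose itself; the passages need to be reconciled.

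**What to change.** 1. In SAP 4.3, define the Safety population as all participants who received any amount of bamlanivimab. Use it for the exposure, AE and SAE, infusion-site, hypersensitivity, vital-sign and IPD outputs, and for the term in Table 4.1.
2. For the primary proportion, use all treated patients, in line with SAP 3.4, 4.1 and the precision statement on 109. State how treated patients with no follow-up for the endpoint are counted.
3. In SAP 4.9, declare that the primary set differs from the protocol Efficacy set, which also requires a post-baseline measure for the endpoint.
4. If the current 4.3 set is kept at all, label it a sensitivity set, and report how many of the 109 it excludes and why. This is optional, and redundant if it excludes nobody.

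The cost is a few SAP sentences and one population flag. No new data are needed.
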